Terminology Criteria for Adverse Events (CTCAE version 5.0). **Statistical Methods:** Sample size: Sample size was calculated to compare the proportion of participants who become positive to SARS-CoV-2 RT-PCR within 1 month after randomisation between the two groups: Placebo group and experimental group receiving ivermectin up to D28. Based on a study assessing the transmission of SARS-CoV-2 infections in households carried out in the US between April and September 2020, the proportion of randomised participants becoming infected in the placebo group is estimated to be 54% (Grijalva et al, 2020).. A difference of 20% is expected between the two groups (OR=2.28). With a power of 90% (1- β) and a significance level of 5% (α), according to the Casagrande & Pike formula the required sample size to detect such difference with a test of comparison of two proportions is equal to 138 participants per arm (Casagrande et al, 1978). A total of 396 participants (198 per arm), rounded up to 400 participants (200 per arm) is required to account for the primary analysis. This sample size also accounts for an estimated dropout rate of 30%. Primary endpoint analysis: The comparison of proportion of participants who were tested positive for SARS-CoV-2 up to D28: placebo group versus ivermectin group, will be performed using the Cochran-Mantel Haenszel (CMH) chi-squared test at the two-sided 0.05 level. Twosided 95% confidence intervals (95% CI) for the proportion differences between groups will be provided. Odds-ratio and corresponding 95% CI will also be reported. The primary endpoint will also be analysed using a logistic regression with treatment group and country as a covariate. Moreover, the analysis of the primary endpoint will be performed for the PP population.

Clinical Protocol

Safety analysis:

Safety will be pooled analyses for the Safety set from all centres and countries. Placebo and ivermectin groups will be compared.

All adverse events (AEs) will be coded according to coding dictionaries (MedDRA, applicable version) and summarised at System Organ Class (SOC) and Preferred Term (PT) levels. AEs will be classified according to period of occurrence: pre-treatment AEs, treatment-emergent AEs (TEAEs) and post-treatment AEs (PTAEs). AE reporting will focus on TEAEs and PTAEs. Incidence of TEAEs and PTEAEs will be summarised and detailed by seriousness, intensity, action taken with the study medication, other action taken and relationship to study treatment.

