1.3 Study design

This is a randomised, double blind, parallel-group, placebo-controlled, multicentric Phase II clinical trial evaluating the efficacy and safety of ivermectin tablets in the prevention of COVID-19 infection.

If all eligibility criteria are met, the participant will be randomised, and a loading treatment dose will be administered.

Participants will be assigned in a 1:1 ratio to receive oral daily treatment with either ivermectin or placebo. Randomisation will be performed stratified by country.

The study requires two visits to the study center, on Day 1 and Day 28, the first and last days of treatment. In addition, there will be 3 remote visits (day 4, day 7 and day 10) that can be conducted by telephone.

The treatment period lasts for 28 days in total, followed by a 28-day follow-up period, and there is a 2-day window period for visits. Therefore, total study duration for each participant is up to 58 days.

Ivermectin will be supplied as 3 mg tablets and will be administered orally, under fasting conditions, as follows: 200 ug/kg as the loading dose on Day 1 and then 100 ug/kg/day for

Statistical Analysis Plan	Version 1.0		Page 7 of 25
Sponsor	MedinCell	Protocol No	mdc-TTG-CT-002

27 days. Control participants will receive placebo tablets, the number of tablets to be taken will match the number of IVM tablets taken by the active participants in the same body weight range.

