4.6.2 Secondary endpoints

Statistical Analysis Plan	Version 1.0		Page 15 of 25
Sponsor	MedinCell	Protocol No	mdc-TTG-CT-002

The analysis of the secondary endpoints is purely explorative.

Results of RT-PCR tests and time to a positive test will be performed on the mFAS and PP population, while the analysis related to the occurrence of symptoms, (related) adverse events are performed on the FAS and PP population.

Treatment comparisons on proportions will be done using Cochran Mantel Haenszel chi-square test presenting odds-ratios, relative risk, and risk differences with 95% confidence intervals. Country will be used as a stratification factor. In case the study was only performed in one country, the Chi-squared/Fisher's exact test will be used.

Comparisons between treatment groups on time to events will be done by using a Cox proportional hazard model, under the assumption of proportional hazards. Time-to event curves will be created for visualization. Hazard ratios with 95% CI will be presented, together with the P-values. Censoring will be at study completion or at discontinuation date (including date of death, if occurring).

Treatment comparisons on mean score (WHO COVID-19 and NEWS-2) will be performed per time point by means of the t-test. If normality cannot be assumed based on visual inspection, a non-parametric alternative will be used.

Statistical Analysis Plan	Version 1.0		Page 16 of 25
Sponsor	MedinCell	Protocol No	mdc-TTG-CT-002

Treatment comparisons on durations will be examined by means of the non-parametric Wilcoxon-Rank-Sum test. If normality can be assumed based on visual inspection, a parametric alternative will be used.

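### The Cox models in SAP 4.6.2 omit country, the randomisation stratum: a minor gap that costs some power only if treatment works and countries differ in infection risk

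*SAP*

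**What the plan says.** SAP 1.3 fixes the allocation: "Participants will be assigned in a 1:1 ratio to receive oral daily treatment with either ivermectin or placebo", and "Randomisation will be performed stratified by country".

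Country then enters three analyses of proportions. The primary CMH test in SAP 4.6.1 is stratified by it. So are the secondary proportions in SAP 4.6.2: "Country will be used as a stratification factor". The protocol synopsis adds it to a supporting model: "The primary endpoint will also be analysed using a logistic regression with treatment group and country as a covariate".

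The next paragraph of SAP 4.6.2 covers time to event: "Comparisons between treatment groups on time to events will be done by using a Cox proportional hazard model, under the assumption of proportional hazards". It promises hazard ratios, confidence intervals and P-values and gives a censoring rule, but does not mention country. The sentence on stratification belongs to the preceding paragraph, on proportions.

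Two statements in the same section limit the point: "The analysis of the secondary endpoints is purely explorative", and "In case the study was only performed in one country, the Chi-squared/Fisher's exact test will be used".

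**The concern.** A programmer who follows the time-to-event paragraph literally would fit treatment group alone, both for time to positive RT-PCR and for time to first COVID-19 related clinical event.

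Where baseline hazards differ between countries, that model pools unlike hazards. Suppose the treatment effect is constant within each country. High-risk participants are used up faster on placebo than on ivermectin, so the mix of countries still at risk drifts apart between the arms. The pooled hazard ratio then moves toward 1 over time, and the proportional hazards assumption that the paragraph invokes no longer holds exactly. The model's standard error also ignores the balance that stratified randomisation creates.

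At stake are a somewhat diluted hazard ratio and some lost power for the first-listed secondary objective, time to RT-PCR positivity. The text also leaves room to add or drop country once results are known.

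**Working it through.** **1. The plan's own figures.** Inputs: in the protocol synopsis, "the proportion of randomised participants becoming infected in the placebo group is estimated to be 54" per cent, with a 20-point difference, so 34% on ivermectin. Power is 90% and alpha 5% two-sided.

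- OR = (0.54/0.46)/(0.34/0.66) = 2.28, as stated.
- Uncorrected n = [1.96·√(2·0.44·0.56) + 1.2816·√(0.54·0.46 + 0.34·0.66)]² / 0.20² = 127.4, so 128.
- With continuity correction, n = (127.4/4)·[1 + √(1 + 4/(127.4·0.20))]² = 137.2, so 138 per arm, as stated.
- 138/(1 − 0.30) = 197.1, so 198 per arm, as stated.

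The documents give no power, event count or hazard ratio for the Cox models.

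**2. The implied Cox setting.** HR = ln(0.66)/ln(0.46) = 0.535. Expected events = 138·(0.54 + 0.34) = 121. Schoenfeld power = Φ(√(121.4/4)·|ln 0.535| − 1.96) = Φ(1.49) = 93%.

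**3. Size of the drift (illustration).** Take two equal countries with placebo risks of 34% and 74%, and HR 0.535 within each. Over 28 days the placebo cumulative hazards are −ln 0.66 = 0.416 and −ln 0.26 = 1.347.

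- Uninfected at day 28 on placebo: 0.66 and 0.26, so the high-risk country makes up 0.26/0.92 = 28% of those at risk.
- On ivermectin: 0.66^0.535 = 0.801 and 0.26^0.535 = 0.486, so it makes up 0.486/1.287 = 38%.
- Pooled hazard ratio at day 28 = 0.535·(0.622·0.416 + 0.378·1.347)/(0.717·0.416 + 0.283·1.347) = 0.61, against 0.535 at the start.

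**4. Simulation, continuous infection times.** 138 per arm, 1:1 within country, exponential times censored at day 28, HR 0.535 within each country, 4,000 trials per case. Countries are of equal size unless noted. Country numbers, shares and risks are assumptions.

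| Placebo risks | HR without / with country strata | Power without / with |
|---|---|---|
| 54/54% | 0.53 / 0.53 | 93% / 93% |
| 44/64% | 0.543 / 0.536 | 91% / 92% |
| 34/74% | 0.56 / 0.53 | 90% / 93% |
| 34/54/74% | 0.56 / 0.54 | 91% / 93% |
| 56/34%, split 90/10 | 0.54 / 0.53 | 93% / 93% |
| 5/15% | 0.52 / 0.52 | 25% / 26% |
| 20/88% (extreme) | 0.63 / 0.53 | 79% / 94% |

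With no treatment effect the hazard ratio stays at 1. Rejection without country is 4.8% (44/64), 3.3% (34/74) and 0.6% (20/88), against about 5% with strata. The reason shows in the 34/74 case: the unstratified model reports a mean standard error of 0.164 for the log hazard ratio, while the actual spread is 0.149.

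**5. Simulation on the trial's test schedule.** The set-up is the same, with infection detected only at D4, D7, D10 or D28, Efron handling of ties and 2,000 trials per case.

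| Placebo risks | Power without / with country strata |
|---|---|
| equal | no difference |
| 44/64% | 93% / 94% |
| 34/74% | 89% / 93% |
| 20/54/85% | 86% / 93% |

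A repeat at 34/74% gave 89% against 92%, so the loss there is about 3 points, in line with step 4. The Monte Carlo standard error of one power figure near 90% is √(0.9·0.1/2000) = 0.7 points.

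**The case against.** The strongest reply is that little hangs on this. The SAP labels the secondary analyses exploratory, and no decision rule or power claim rests on the Cox models. The trial may run in one country, where the issue vanishes. Every participant is a recent close contact of a PCR-confirmed case, so risk depends largely on transmission given exposure, and nothing in the documents shows that countries differ. The SAP is also silent on country for these models, which is not the same as excluding it, and the protocol text available is only the synopsis and schedule. All of this stands. It limits the size of the point, but the model still needs to be stated.

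A reader might go further and infer three things that the documents do not support.

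- *The Cox result could disagree with the primary test only because country was left out.* The two differ in any case: SAP 4.1.2 restricts multiple imputation to the primary endpoint. Adding country would not put them on one footing.
- *The planned model gives a diluted hazard ratio and too little power, without condition.* Dilution needs both a real effect and differing country risks. Larger losses do appear with a weaker effect: at HR 0.60, power is 77% against 82% for risks of 35/73%, and 68% against 80% for 20/54/85%. But 0.60 is not the effect that the design implies.
- *False positives rise.* The simulations show the opposite.

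**Conclusion.** The point holds as a minor, conditional one. As written, the Cox models omit the stratum used in randomisation and in the CMH comparisons. At the design's own effect the cost is about 1 point of power for placebo risks of 44/64%, about 3 for 34/74% and about 7 for 20/54/85%. There is no cost if risks are equal or only one country enrols, and almost none if one country dominates or infection is rare everywhere.

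These sizes assume a constant hazard ratio within countries, constant hazards over 28 days, 138 evaluable participants per arm and equal-sized countries. Only the first-listed time-to-event endpoint, RT-PCR positivity, was sized. Time to first clinical event was not, because the documents give no event rate for it. Neither the primary CMH test nor the sample size is affected.

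**What to change.** Add to the time-to-event paragraph of SAP 4.6.2:

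> Cox models will be stratified by country (separate baseline hazards, common treatment effect); if only one country takes part, no stratification is used.

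Apply it to both time-to-event endpoints. The single-country clause mirrors the fallback already written for the CMH tests. SAP 2.1 provides for amendment before database lock and unblinding, which is when this should be settled.

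The cost is one sentence and one STRATA statement, with no new data. In the simulations it cost no power when countries were alike. There is one small downside: for endpoints with few events, or with very small countries, strata with participants at risk in only one arm contribute no information. The blinded data review is a natural place to check for this and, if needed, to fix a rule for combining small countries before unblinding.

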RT-PCR tests on D4, D7, D10, and D28, and at any unscheduled visits. Secondary endpoints analyses: RT-PCR tests on D4, D7, D10, and D28, and at any unscheduled visits. WHO COVID-19 and News 2 scales scoring on D1, D10, and D28, and at any unscheduled visits. COVID-19 related AE notification by participants and/or investigators throughout the study. COVID-19 related hospitalisations notified by the investigators. Duration of hospitalisation as calculated from the associated SAE notification form (date of hospital admission through to date of hospital release). COVID-19 related deaths notified by the investigators. AE notification by participants or detection by investigators. **Concomitant Medication:** Prohibited medications: The following medications are prohibited: Inhibitors of p-glycoprotien, e.g. amiodarone, azithromycin, ketoconazole, cyclosporine up to 28 days prior to randomization and throughout the study. Current pain medications such as acetylsalicylic acid or metamizol. Precautions: Some medications may have moderate or minor interactions with ivermectin. **Endpoints:** Primary endpoint: Proportion of laboratory-confirmed COVID-19 infections between baseline and Day 28. Secondary endpoints: Time to change from baseline in negative RT-PCR to positive RT-PCR. Change from baseline in the WHO-COVID 19 and NEWS-2 scores. Time to change from baseline to first COVID-19 related clinical events. Proportion of COVID-19 related hospitalisations. Proportion of COVID-19 related mortality. Safety and Tolerability of ivermectin based on treatment emergent adverse events (TEAE) and serious adverse events (SAE) according to Common

Clinical Protocol

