2 GENERAL INFORMATION

2.1 Background details

All study data will be transferred to a SAS database (version 9.4 or later, SAS institute, North Carolina, USA) for statistical analysis purposes. Data will be imported from a Data Capture System IBM Inform via validated SAS programs.

The SAP will be finalized before the interim analysis, any changes needed after the DMC meeting will lead to an SAP amendment which needs to be finalized before database lock and unblinding after agreement with the Sponsor on subject disposition and coding.

Statistical Analysis Plan	Version 1.0		Page 8 of 25
Sponsor	MedinCell	Protocol No	mdc-TTG-CT-002

Deviations from the protocol will be judged during the study and/or when an individual participant's CRF is completed (monitored).

Before unblinding the data, a blinded data review meeting (BDRM) will take place where protocol deviations will be classified (major/minor protocol deviations) for statistical analysis. Intake of pain medications such as acetylsalicylic acid and metamizole, will not be considered a major protocol deviation.

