4 STATISTICAL ANALYSES

All statistical analyses will be performed using the SAS® software (Version 9.4 or later, SAS institute, North Carolina, USA).

All descriptive statistics will be given by treatment group. For baseline and basic variables, they will also be given for the entire analysis set. Screening failure data will not be analysed.

If not stated otherwise the following standard types of descriptive analyses will be presented:

- Descriptive statistics for continuous data

Statistical Analysis Plan	Version 1.0		Page 10 of 25
Sponsor	MedinCell	Protocol No	mdc-TTG-CT-002

N, mean, SD, min, lower quartile, median, upper quartile, and max will be presented. These descriptive statistics will be determined for measured values and optionally for differences to baseline.

Descriptive statistics for categorical data

Absolute frequencies and percentages will be presented. Percentage bases (denominators) will be identified in the table title or footnote (i.e. all subjects at risk, all cases). For changes from baseline, shift tables may be generated.

Inferential statistics

Unless otherwise stated, all statistical tests will be performed two-sided and at a type I error probability of α =0.05.

Unless otherwise stated, all confidence intervals (CIs) will be derived two-sided and at a confidence probability of $1-\alpha=0.95$.

Listings

All recorded data will be listed by subject sorted by treatment group. Identification variables are centre number, participant number and treatment.

Derived data will be stored in special analysis data sets and will be calculated as outlined in section 6.1.

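### SAP 4.6.2 names neither a tie method nor, in the text supplied, the event date for time to RT-PCR positivity; a Breslow approximation would pull the hazard ratio modestly toward 1

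*SAP*

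**What the plan says.** The endpoint is the time from a negative baseline RT-PCR to a positive one (protocol synopsis, Endpoints). The synopsis, under Criteria for Evaluation, lists the tests as "RT-PCR tests on D4, D7, D10, and D28, and at any unscheduled visits". Table 1 allows a window of ±1 day at D4, D7 and D10 and +2 days at D28, and its footnote (d) says that unscheduled tests are collected too. No PCR is scheduled in the 18 days between D10 and D28.

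For the analysis, SAP 4.6.2 says: "Comparisons between treatment groups on time to events will be done by using a Cox proportional hazard model". It will report hazard ratios, 95% confidence intervals and p-values, with PCR times analysed in the mFAS and PP populations. The same section describes all secondary analyses as exploratory.

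On software, SAP 2.1 says only "All study data will be transferred to a SAS database", and SAP 4 repeats that SAS 9.4 or later will be used. No procedure or tie option is named. SAP 4 sends the reader to a Section 6.1 for derived data; that section is not in the text supplied.

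**The concern.** Infection is observed only as having occurred between two tests. If the event time is the nominal visit day, every scheduled positive falls on one of four values. The Cox partial likelihood assumes distinct event times, and the usual approximations for ties differ when a large share of the risk set fails at the same time. Breslow's keeps all tied cases in the risk set for each other's contribution, which pulls the estimate toward 1. Efron's removes them progressively.

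With ties this heavy, the reported hazard ratio depends on a choice that the SAP leaves open. At stake are some shrinkage of the estimate for the first-listed secondary objective, a slightly conservative test, and an analyst's choice that could be made after unblinding.

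**Working it through.** **1. The plan's own figure.** The inputs, from the synopsis (Statistical Methods) and SAP 1.4, are 54% infected on placebo, a difference of 20 points, two-sided α of 0.05 and 90% power. The stated OR of 2.28 shows that the difference is absolute: (0.54/0.46)/(0.34/0.66) = 2.28.

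- A = [1.960·√(2·0.44·0.56) + 1.2816·√(0.54·0.46 + 0.34·0.66)]² = 5.094.
- Casagrande–Pike: n = A/(4·0.2²)·[1 + √(1 + 4·0.2/A)]² = 137.2, so 138 per arm.
- With 30% not evaluable: 138/0.70 = 197.1, so 198 per arm and 396 in total.

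All of this agrees with the plan. The documents give no hazard ratio, event count or power for the Cox analysis.

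**2. Hazard ratio implied by the planning rates.** Under proportional hazards, HR = ln(1 − 0.34)/ln(1 − 0.54) = ln 0.66/ln 0.46 = 0.535 (log HR −0.625).

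**3. How heavy the ties are.** About 140 of 200 per arm are evaluable, so the expected positives are 140·0.54 + 140·0.34 = 75.6 + 47.6 ≈ 123 among 280.

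**4. Large-sample Breslow estimate.** At visit j, let r be the fraction at risk and d the fraction newly positive, in the control (c) and treated (t) arms. The Breslow estimate θ solves

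Σ d_t = Σ (d_c + d_t)·θ·r_t/(r_c + θ·r_t).

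Worked case: positives on placebo split equally over the four visits, and treated survival = control survival^0.535. The last column uses θ = 0.559.

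| Visit | r_c | r_t | d_c | d_t | Expected in treated arm |
|---|---|---|---|---|---|
| D4 | 1.000 | 1.000 | 0.135 | 0.0747 | 0.0752 |
| D7 | 0.865 | 0.925 | 0.135 | 0.0803 | 0.0806 |
| D10 | 0.730 | 0.845 | 0.135 | 0.0876 | 0.0875 |
| D28 | 0.595 | 0.757 | 0.135 | 0.0974 | 0.0967 |
| Sum | | | | 0.340 | 0.340 |

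The equation balances at 0.559, not at 0.535.

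**5. Varying the visit distribution.** The documents do not say how positives divide over the visits, so these splits are assumptions. The "spread" columns put each visit's positives evenly on three successive days.

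| Share at D4/D7/D10/D28 | Breslow, nominal | Log HR lost | Efron, nominal | Breslow, spread | Log HR lost, spread |
|---|---|---|---|---|---|
| 25/25/25/25% | 0.559 | 7% | 0.536 | 0.544 | 3% |
| 50/25/15/10% | 0.564 | 8% | 0.536 | 0.546 | 3% |
| 20/20/20/40% | 0.564 | 9% | 0.536 | 0.546 | 3% |
| Constant hazard (19/13/12/55%) | 0.575 | 11% | 0.537 | 0.551 | 5% |
| 10/10/10/70% | 0.589 | 15% | 0.539 | 0.557 | 6% |

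Log HR lost = 1 − ln(Breslow)/ln(0.535). Efron with spread dates is also 0.536 to 0.539.

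**6. Lower infection rates, same true HR, nominal days, 50/25/15/10% split.** Breslow gives 0.540, 0.544 and 0.549 at placebo rates of 10%, 20% and 30%. Efron gives 0.535 at each.

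**7. Effect on inference.** Simulation with 140 per arm, nominal days, 600 runs per scenario and no dropout between visits, testing as in SAP 4 ("all statistical tests will be performed two-sided and at a type I error probability of α =0.05"):

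| Scenario | Breslow rejects | Efron rejects | Breslow 95% CI coverage |
|---|---|---|---|
| 50/25/15/10% | 90.8% | 93.0% | 95.0% |
| 25/25/25/25% | 90.2% | 91.5% | 95.3% |
| 20/20/20/40% | 92.5% | 94.5% | 95.8% |
| No effect, 50/25/15/10% | 2.0% | 3.8% | 98.0% |

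Under no effect, Breslow gives an HR of 1.00. Its standard error errs on the large side: in the first scenario the mean model value is 0.186 against an empirical SD of 0.166. That is why coverage holds although the estimate is shifted. A grouped-time complementary log-log model gave 0.526 to 0.536 in the three effect scenarios, against 0.528 to 0.538 for Efron in the same runs.

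**The case against.** The strongest objection is that the bias depends on something the documents do not contain. They name SAS, but no procedure, no tie option and no intention to use defaults; the sentence in SAP 2.1 is about data transfer. A reader might infer that the planned hazard ratio will be biased. The text does not support that: with Efron ties there is essentially no bias. This stands, and the result is therefore conditional on Breslow.

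Second, part of the silence may come from missing text. SAP Section 6, to which SAP 4 refers for derived data, is absent from what was supplied and may define the event time. That also stands, so the missing event date can only be said of the text supplied. It does not settle the tie method, which belongs with the model in 4.6.2 and is not stated there.

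Third, four tied days is the extreme case. If actual dates are used, visit windows and unscheduled tests spread the events and cut the shift by more than half. The 54% comes from a household study, whereas this trial also admits non-household contacts and analyses the endpoint in participants who were PCR-negative at baseline. A lower rate means a smaller shift.

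Fourth, a reader might conclude that the Cox model is wrong for visit-based data or that its interval is invalid. Neither follows: Efron recovers the hazard ratio on the same grouped data, and Breslow coverage was 95 to 96% in the effect scenarios simulated.

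**Conclusion.** The point holds as a conditional one. The tie method is unspecified for a heavily tied endpoint, and the event date is unspecified in the text supplied. If Breslow is used at the planning rates, the hazard ratio moves from 0.535 to about 0.56–0.59 on nominal days, a loss of 7 to 15% of the log HR. With dates spread over the windows it moves to about 0.54–0.56. The nominal-day shift is 0.045 to 0.096 on the log scale, about a quarter to a half of a standard error of 0.19. Power falls by about 2 points where simulated. The direction is conservative.

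This rests on four assumptions: Breslow as the method in use, the visit distribution, proportional hazards, and the planning rates. The most late-weighted and constant-hazard splits were solved only in the large-sample limit, so power and coverage were not checked there.

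The result applies to time to RT-PCR positivity. It does not carry over directly to time to first clinical event, which is not tied to the PCR visits, and it has no bearing on the primary CMH test.

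**What to change.** Add one sentence to SAP 4.6.2 for time to RT-PCR positivity: state whether the event time is the nominal visit day or the actual test date, and specify TIES=EFRON (or TIES=EXACT) in the Cox model. If Section 6 already defines the event time, a cross-reference is enough for that part.

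A grouped-time complementary log-log model, with visit-interval terms, treatment and country, is an optional alternative that estimates the same hazard ratio. It is not quite free: it needs a rule for assigning unscheduled tests to intervals, and it gives up their exact dates.

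The Efron or exact option changes nothing in data collection, sample size or conduct. Label: free improvement.
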